established in 1994 to improve and strengthen the processes for managing communicable and non-communicable diseases, reorienting the system on preventive services. The Department for Regional Public Health Management within the NCDC, directed by **[name] (co-I)**, oversees the 68 local public health centers, which are municipal public units. These centers manage programs regarding communicable disease prevention, chronic disease management, and healthy living, as well as measures and activities to meet the health needs of the population living in particular areas. **Public health services in AM** evolved from the 1992 Law on Sanitary-Epidemic Safety. In 2002, the country's sanitary and epidemiological services were reorganized as the State Hygiene and Anti-epidemic Inspection under the Ministry of Health. It consists of a headquarters office and seven operations offices in Yerevan as well as 10 regional offices and several additional local public health centers and other facilities within the local municipalities. In the proposed study, directors of these local public health centers will serve as or identify key leaders to engage in the coalition trainings and lead coalition activities.

*Our study will define a “community” as a distinct municipality, given the division of communities based on the coverage area of the local public health centers. We will include communities with small to medium populations and local public health centers with sufficient capacity to engage in the proposed research. Our partners in GE and AM have identified 14 municipalities within each country fitting these criteria, with populations ranging from ~6,000 to 90,000. An example of GE municipalities and their populations, distances from Tbilisi, and budgets are listed in **Appendix A**. After confirming interest with local health center directors, we will form matched pairs in each country based on population size, region, and local economy and then randomly select one from each pair as an intervention community and the other as a control. We will use block randomization by country. Randomization will occur after completion of the baseline population-level survey.*

[figure not shown]
Condition Description. In brief, all 28 communities (14/country) will participate in the population-level tobacco survey at baseline and follow-up. Within each country, 7 communities will be randomized to the intervention condition and 7 to the control condition (i.e., 14 communities/condition).

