Both qualitative and quantitative analysis will be used. Qualitative analysis will involve a multiple case study of six coalitions (a high, medium, and low performer in each country with performance defined by number of policies passed). After reviewing a subset of the interview transcripts (translated to English), the evaluation teams from the two countries, plus the George Washington University research team, will meet to discuss their general findings and to develop a codebook, using the conceptual model as sensitizing constructs. Once the team is coding consistently (examining transcripts from across countries), one team member in each country will code independently. Any discrepancies in the coding will be discussed and resolved. We will use standard content analysis methods to identify themes, as well as site-ordered matrices based on level of implementation to identify patterns of factors influencing implementation. Community name and participant roles will be identifiable during the analysis phase. While individual study participant names will not be included, it may be possible to identify respondents and/or partners based on information available in the qualitative transcripts. [name] has led several multiple case studies.^{29,98,115}

Power Calculation. We will use coalition member survey data to assess the extent to which CCAT propositions are supported by our data. Many CCAT constructs are conceptualized at the coalition level, which implies a sample size of 14 for these analyses. At the organizational-level, 14 communities will give us sufficient power to detect large effects, specifically $d \geq 0.80$ in paired t-tests and $\rho \geq 0.55$ in correlations ($\alpha=.10$).

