Analyses. We will conduct all analyses for Aim 2 at the community-level (i.e., coalition-level average scores will be created for all models). This analysis strategy is preferable over individual analyses that account for clustering because we aim to understand the coalition impact, compared to individual impact, on policy.^{30,33} We will report univariate properties first and then assess relationship strengths using t-tests and correlations. Due to the small sample size ($N=14$), we will set alpha at .10 as others have done in coalition research.^{30,33,116} We will use chi-square tests, t-tests, and Spearman correlations to assess bivariate relationships. Based on these analyses, we will conduct multivariable regression analyses to identify which contextual (e.g., country) and coalition factors from our conceptual model predict intermediate outcomes, such as member participation and satisfaction, action plan quality, and number of smoke-free policies passed, with a small set of predictors.

I. TRAINING

Emory research staff training for the study will review basic principles and focus on procedures specific to the protocol. Similar trainings will occur at the GE NCDC, the AM NIH, and AUA for all study staff. Training will cover: (1) sampling strategy and recruitment, (2) eligibility confirmation for potential participants, (3) survey and interview data collection, (4) adverse event handling and reporting, (5) data safety and monitoring, (6) protocol adherence. We will establish security procedures (outlined below in Confidentiality). All study staff members will obtain CITI training certificates.

J. PLANS FOR DATA MANAGEMENT AND MONITORING

Given the nature of the research, requiring minimal invasive assessments and no interventions, we have determined that there is no need for a data safety and monitoring board.

K. CONFIDENTIALITY

With regard to minimizing risk of loss of confidentiality or privacy, confidentiality will be protected at all times and potential risks minimized systematically.

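### Chi-square tests at alpha .10 on 14 coalitions rest on an approximation that fails at this size: in a 2x2 table the true level can range from well below .10 to about .13–.15

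*Combined protocol and SAP*

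**What the plan says.** The relevant text is in section H (Data Analysis), under the heading For Aim 2: Coalition Assessment.

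- **Unit and number.** The Analyses paragraph states "We will conduct all analyses for Aim 2 at the community-level", and that "coalition-level average scores will be created for all models". The Power Calculation paragraph says that many constructs sit at coalition level, "which implies a sample size of 14 for these analyses".
- **Alpha.** Because the sample is small, "we will set alpha at .10 as others have done in coalition research".
- **Tests.** "We will use chi-square tests, t-tests, and Spearman correlations to assess bivariate relationships". Multivariable regressions with a small set of predictors are then built on these bivariate results, to "identify which contextual (e.g., country) and coalition factors from our conceptual model predict intermediate outcomes".
- **Split by country.** Section C (Design) says "Within each country, 7 communities will be randomized to the intervention condition and 7 to the control condition". Only intervention communities have coalitions, so the 14 divide 7 and 7 by country.

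The plan gives no continuity correction, exact test, minimum expected count or other rule for sparse tables. The Aim 2 power statement covers paired t-tests and correlations only.

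**The concern.** The chi-square test takes its p-value from a large-sample distribution. The usual guide for relying on it is an expected count of at least 5 in each cell, and 14 units cannot supply that in any 2x2 table. The plan has already relaxed alpha to .10, and a reader will take .10 as the error rate of each such test. If the real rate differs, that reading is wrong.

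Two things follow. First, the bivariate results inform which factors enter the regressions, and with 14 units a single spurious predictor carries weight. Second, the version of the test is left open. Corrected and uncorrected forms err in opposite directions here, so an analyst could choose between them after seeing the data.

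**Working it through.** **Inputs from the protocol.** 14 coalitions; alpha .10; a 7 v 7 split by country; a chi-square test with no version stated. **Assumption.** The common underlying proportion π of coalitions with the characteristic is not in the documents, so it is scanned from 0.001 to 0.999.

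**1. The plan's own figures.** There is none for chi-square. The Aim 2 power paragraph gives detectable effects of d = 0.80 (paired t) and ρ = 0.55 (correlation) at alpha .10 without a target power. With n = 14, two-sided, these correspond to power of about 88% and 66–69% respectively. They have no bearing on whether the chi-square test holds its level.

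**2. Expected counts.** The smallest expected count in a 2x2 table is (smaller row total × smaller column total)/14. Each smaller total is at most 7, so the maximum is 7 × 7/14 = 3.5.

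**3. Exact size at 7 v 7.** Let a and b be the numbers with the characteristic in the two countries, and s = a + b. Uncorrected Pearson reduces to

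X² = 14(a − b)² / [s(14 − s)], rejecting when X² ≥ 2.706.

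The true level is the sum of C(7,a)·C(7,b)·π^s·(1 − π)^(14 − s) over the rejected tables among the 64 possible.

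With a < b, the rejected tables are 0 v 3 or more, 1 v 4 or more, 2 v 6 or 7, 3 v 6 or 7, and 4 v 7; their mirror images are also rejected. At π = .5 the sum can be done by hand:

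- a = 0: 35 + 35 + 21 + 7 + 1 = 99
- a = 1: 7 × (35 + 21 + 7 + 1) = 448
- a = 2: 21 × (7 + 1) = 168
- a = 3: 35 × (7 + 1) = 280
- a = 4: 35 × 1 = 35

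The total is 1,030. Doubling for the mirror images gives 2,060/2¹⁴ = 2,060/16,384 = .126.

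The same sum at other values of π:

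| π | .1 | .2 | .3 | .4 | .5 |
|---|---|---|---|---|---|
| True level, nominal .10 | .027 | .087 | .125 | .130 | .126 |

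The level exceeds .10 for π between about .23 and .77. The maximum is .130, near π = .37.

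**4. Where the excess arises.** For 1 of 7 against 4 of 7, X² = 14 × 9/(5 × 9) = 2.80, which is just significant at .10. Given those margins, the exact two-sided probability of a table at least this extreme is 2 × (21 + 245)/2,002 = .266.

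**5. Other tables (uncorrected Pearson).** Maximum level by split: 6:8 .126, 5:9 .139, 4:10 .116, 3:11 .150, 2:12 .097, 1:13 .105. A 2x3 table by country with three equally likely categories gives about .124.

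**6. Alternatives at nominal .10.**

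| Test | Maximum level, 7 v 7 | Elsewhere |
|---|---|---|
| Yates-corrected chi-square | .024 | at most .027 over all splits |
| Fisher's exact | .024 | .075 at 4:10 |
| Fisher mid-p | .075 | .109 at 6:8 |
| Boschloo | .075 | .066 at 6:8; .093 at 3:11 |

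At 7 v 7 Boschloo differs from Pearson only in not rejecting 1 v 4 and 3 v 6 (and their mirrors). Each carries weight 245 in step 3, so at π = .5 the level becomes 2 × (1,030 − 490)/16,384 = .066.

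**7. Power for .8 v .2 at 7 v 7.** Pearson .79 (at its inflated level), Boschloo .71, Fisher and Yates .50.

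**The case against.** The strongest reply is about relevance. The protocol names no 2x2 table. Country is its only named two-level factor, and the intermediate outcomes it lists are participation, satisfaction, action plan quality and number of policies passed. These are averages, scores or counts, which call for t-tests or correlations. Chi-square appears once, in a general list. The most natural categorical table, country by committee complexity (coded 1 to 3), is 2x3. This stands, and it limits the importance of the point. It does not remove it, because the test is in the plan and a 2x3 table by country with equal categories shows a similar excess (.124).

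The second reply is that .130 is a worst case. Averaged over an even grid of proportions, the 7 v 7 level is .086. This also stands. A reader might infer that these tests simply run at 13% instead of 10%. The documents do not support that: they give no proportion and no version of the test, and both decide whether the level is above or below .10.

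The third reply is that, in exploratory screening of 14 units, accepting some excess error to keep power is a legitimate judgement. That is fair, and the exact test does cost power. But the plan states alpha as .10 and does not present a higher rate as a deliberate choice.

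**Conclusion.** The point holds as a minor one. The chi-square test is not reliable at its stated level with 14 units. Uncorrected, at 7 v 7, the level runs from far below .10 at extreme proportions to .130, and a 3:11 split can reach .150. With Yates's correction it stays at or below .024 at 7 v 7. The plan does not say which form applies.

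These figures rest on independent coalitions, a common proportion that had to be assumed, and rejection at nominal .10. The bound of 3.5 applies to the smallest expected count in a 2x2 table, not to every cell. Beyond 2x2, only the 2x3 case by country with equal categories is quoted.

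A reader might also infer that the Aim 2 conclusions, or the trial's main result, are compromised. Neither follows. The primary comparison is Aim 1, which uses multilevel models on the population survey. Within Aim 2, chi-square is one of three listed bivariate tests, and few of the named measures need it.

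**What to change.** In the Aim 2 Analyses paragraph of section H, replace the reference to chi-square tests with: *Boschloo's unconditional exact test for 2x2 tables and exact permutation tests for larger tables*. Boschloo's test takes Fisher's p-value as its statistic and maximises over the unknown proportion, so it cannot exceed the nominal level. Its maximum was .066 to .093 over splits from 7:7 to 3:11.

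Fisher mid-p should not be offered as an equivalent, because it exceeds .10 at 6:8. The ordinary Fisher test holds the level but gives up much more power at 7 v 7.

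The cost is one sentence, with no new data and no change of design, plus somewhat lower power than the uncorrected test: .71 against .79 in the example above.

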- **Aim 2.** Assess how community context and coalition factors influence adoption and implementation of organizational and municipal smoke-free policies to provide an evidence-base for public health practice.
- **Aim 3.** Disseminate research findings regarding both the effectiveness and the process of establishing and maintaining coalitions, and consequently increasing smoke-free policies and reducing SHSe, to key stakeholders in GE and AM in order to inform future tobacco control research and practice efforts.

- **Aim 4.** Capitalize on proposed research and dissemination opportunities to build tobacco control research capacity within the GE NCDC, AM NIH, TSMU, and AUA, as well as practice capacity within local public health centers and their civil society partners.

C. DESIGN

Funder

The project is pending funding by the National Institutes of Health Fogarty International Center.

Participants, setting, recruitment, and procedures

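### Aim 2 bases its regressions on bivariate tests in the same 14 coalitions, so the regression p-values do not carry the stated .10 error rate

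*Combined protocol and SAP*

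**What the plan says.** Section H (Data Analysis, For Aim 2: Coalition Assessment) fixes the unit of analysis: "Many CCAT constructs are conceptualized at the coalition level, which implies a sample size of 14 for these analyses", and "coalition-level average scores will be created for all models". The significance level follows: "Due to the small sample size ($N=14$), we will set alpha at .10 as others have done in coalition research".

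The analysis then has two steps. The first is bivariate: "We will use chi-square tests, t-tests, and Spearman correlations to assess bivariate relationships". The second depends on the first: "Based on these analyses, we will conduct multivariable regression analyses to identify which contextual (e.g., country) and coalition factors from our conceptual model predict" four named outcomes (member participation, member satisfaction, action plan quality, number of smoke-free policies passed). That outcome list is open-ended, and the models are to hold only a few predictors.

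The section does not say how a bivariate result admits a factor to a model, how many factors are screened, or whether any p-value is adjusted. It does not call the regressions exploratory. Section B states the purpose of Aim 2 as "to provide an evidence-base for public health practice", and the Aim 2 power paragraph says the member survey will be used to judge how far the coalition theory's propositions are supported.

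**The concern.** A factor that reaches a model because it was associated with the outcome in these 14 coalitions is then tested again on those coalitions. Its regression p-value is computed as if the factor had been chosen without looking at the outcome. Under the null, such a p-value falls below .10 more than 10% of the time.

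At stake is which coalition and contextual factors the study reports as predictors of policy adoption and member engagement. Those reports feed the theory test and the practice guidance to be disseminated under Aim 3. A reader who sees a coefficient at p<.10 would take it to carry a 10% false-positive risk, and it does not.

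**Working it through.** **Inputs from the protocol**
- 14 coalitions, 7 per country; alpha .10 (section H, Aim 2; section C).
- Ten named candidates. Nine are coalition factors in section D, Assessment 2: representation, communication, decision-making, task focus, cohesion, leadership, staffing, size and complexity. Country is the tenth.
- Four named outcomes (section H).

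**Assumptions, because the protocol is silent**
- Entry at two-sided p<.10.
- Correlation among candidates 0 to .7 and among outcomes 0 to .8.
- Normal outcomes, including the policy count.

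**1. The plan's own figures.** The plan gives no false-positive rate for the two-step procedure, so there is none to reproduce. It gives detectable effects for single tests at alpha .10 (d of 0.80, rho of 0.55) without a power level. With n=14 and two-sided testing these have 88% power (paired t-test) and 69% (exact Pearson). They describe one test at a time and do not address selection.

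**2. Entry threshold.** The two-sided .10 critical value on 12 df is t = 1.782. The matching correlation is r = 1.782/√(1.782² + 12) = .4575. Under the assumed rule, any sample correlation beyond about .46 admits a factor.

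**3. Screening alone, if tests were independent**
- One outcome, ten candidates: 1 − .90^10 = 65.1% chance that at least one null factor passes.
- Four outcomes: 1 − .90^40 = 98.5%, with 40 × .10 = 4 false passes expected.

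These are benchmarks only: they stop at the screen and ignore correlation.

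**4. Screen followed by regression, no true effects.** Simulation of 4,000 studies per row: ten candidates, a t-test for country, all screened factors entered together in ordinary least squares. Entries are the chance of at least one coefficient at p<.10.

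| Candidate corr. | Outcome corr. | Spearman, one outcome | Spearman, any of four | Pearson, any of four |
|---|---|---|---|---|
| 0 | 0 | 46.0% | 91.0% | 96.6% |
| 0 | .8 | 45.0% | 79.5% | 90.0% |
| .5 | 0 | 28.8% | 73.5% | 83.4% |
| .5 | .8 | 30.2% | 63.3% | 73.5% |
| .7 | 0 | 21.0% | 61.1% | 70.7% |
| .7 | .8 | 20.9% | 49.4% | 60.3% |

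The Monte Carlo standard error near one half is √(.5 × .5/4000) = 0.8 points, so repeat runs differ by about a point. Over all runs the summary is about 21% to 48% of single outcomes and 50% to 91% of studies (Spearman), and about 61% to 97% of studies (Pearson).

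**5. Per predictor.** With the Spearman screen, about 23% to 55% of null predictors that enter reach p<.10 in the model, against 10% nominal.

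**6. Sensitivity**
- Capping entry at three predictors changes little: with uncorrelated candidates and outcomes, 92.3% of studies with the cap and 91.0% without.
- Screening five candidates instead of ten gives 43% to 76% of studies (Spearman).

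**7. Does naming predictors in advance help?**
- Two predictors named for one outcome, no screening: simulated per-predictor error .0996, and .18 for at least one (independence gives 1 − .90² = .19).
- Two predictors for each of four outcomes: 1 − (1 − .18)^4 = 1 − .82^4 = 55% if outcomes are independent. Naming predictors restores the per-test error rate; limiting the number of main outcomes is what controls the study-level rate.

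**The case against.** The strongest reply is that no p<.10 entry rule is written. The section speaks of relationship strengths, of factors taken from the conceptual model, and of few predictors, so choice by theory and effect size fits the text. That stands: the threshold is an inference, and every rate above depends on it. It does not remove the problem. The regressions are expressly made to follow from the bivariate results. With all correlations computed on the same 14 coalitions, ranking by strength is in effect ranking by p-value. Figure 1, the conceptual model, was not available in the text reviewed. If it fixes the predictors for each outcome and only those are fitted, the concern shrinks accordingly.

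The promise of few predictors limits the size of the model, not the number of factors screened, and the capped simulation shows little change.

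It can also be said that alpha .10 and N=14 are disclosed and justified, that Aim 2 is secondary, and that it also draws on a six-coalition case study. All true. The criticism is not of .10 as a level, but that the procedure does not deliver it.

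Two stronger readings fail. A reader might infer that a predictor entering alone is bound to stay significant. That holds when the screen and the model use the same test. With a Spearman screen followed by least squares, only about 66% to 73% of lone entrants stay below .10. A reader might also take 80% to 97% of null studies as the headline. That needs Pearson-type screening and independent outcomes, whereas the plan names Spearman, and participation and satisfaction come from the same member survey.

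**Conclusion.** The concern holds in a limited form. As written, the Aim 2 regressions test factors on the data that suggested them, and their p-values do not have the stated .10 error rate. If entry is at p<.10, with ten candidates, four outcomes, a Spearman screen and no true effects, an entering predictor has about a 23% to 55% chance of reaching p<.10. At least one false predictor appears in about 50% to 91% of studies. For a single outcome the figure is about 21% to 48%, so a false report is likelier than not only at study level, and barely so when candidates and outcomes are both highly correlated.

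A reader might infer that most Aim 2 findings would be false. The documents do not support that: the rates assume every effect is null, and the share of false findings depends on how many of the theory's factors truly matter, which is unknown. Nor does the point touch the Aim 1 primary result, which uses the population survey and a separate model. The change should be made, but the trial's main conclusion does not depend on it.

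**What to change.** Amend the Aim 2 analysis paragraph as follows.

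1. Before the outcome data are seen, name one main Aim 2 outcome and at most two predictors for it from the conceptual model. Test only those, without screening. Two tests at .10 leave about an 18% chance of at least one false positive; if .10 is wanted for the pair, use .10/2 = .05 each.
2. For any screened model, take p-values from a permutation test. Shuffle the outcome rows jointly over the 14 coalitions, which keeps the correlation among outcomes. Repeat the whole screening and regression each time, and compare with the permutation distribution of the smallest p-value over all candidates and outcomes. This requires writing down the entry rule, which the plan currently lacks.
3. Report every bivariate correlation with a 90% interval, whether or not it is significant.
4. Label results from screened models hypothesis-generating.

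The cost is some wording and a short script; no new data are needed. The price is fewer nominally significant predictors.
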